# Research Design & Methods (Aim #1, 2, 3)

**Design:** A two-group, randomized controlled trial with three assessment points (baseline, approximately 11 weeks, and approximately 19 weeks) will be conducted. The randomization will be stratified across study sites. Study Locations: We will recruit participants from a total of eight sites. We will have staff at three study sites in VISN8: NF/SG VHS in Gainesville, FL; James A. Haley Veterans Hospital in Tampa, FL; Bruce W. Carter Medical Center, in Miami, FL. Staff at these sites will also recruit from Michael E. Debakey VAMC in Houston, TX, Hunter Holmes McGuire VAMC in Richmond, VA, Central Arkansas Veterans Healthcare System, VA Tennessee Valley Healthcare System, and VA Boston Healthcare System via telephone and mail. All of the sites have large, in-patient hospitals, community living centers, and in-patient rehabilitation units; however, the Tampa site has a standardized, discharge planning process that involves Veteran education while the other sites have no discharge planning process. Thus, the usual/standard discharge planning care that Veterans receive at Tampa may be different than the care received by Veterans at the other sites. The research nurses will document the discharge planning care that the caregivers receive at all sites. In addition, research staff will review the Veterans' CPRS health records and describe the discharge planning care that is documented in the records. To address the issue of potential differences in usual care between study sites, and to aid in recruiting the necessary sample size, we will use a stratified, randomization procedure to achieve balanced group membership across the study sites. In our data analytic plan we will stratify by study sites in addition to controlling for baseline measurements.

Sample: We will recruit a total of 240 caregivers who will be randomized to an intervention or a usual care group (see randomization & power analysis in the data analysis section).

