## **Data Collection:**

Research personnel will follow a step-by-step study procedure manual to collect the data. Research staff will meet or telephone caregivers who are interested in learning more about the study. We will arrange times to meet or talk with the caregivers that are convenient with the caregivers. The research staff will discuss the study and provide the caregivers a copy of the informed consent document, so that they can review it and/or discuss with their family and friends. For caregivers who are willing to participate, the research staff will arrange an in-person or telephone meeting to determine the caregivers' study eligibility (also see inclusion/exclusion criteria & recruitment and enrollment sections). For eligible caregivers, the research staff will meet in person with the caregivers and Veterans or call them to implement the standard consenting process that will be in compliance with VA Central IRB and Research & Development Committees at the 3 study sites. If a discharge date is not known at this time, study staff will call the caregiver on a weekly basis to check on the status of the veteran's discharge.

Once the Veteran and caregiver are enrolled in the study, baseline data will be collected over the phone. If the Veteran is an inpatient at the time of enrollment, baseline data will be collected after the Veteran is discharged. The research staff will ask the caregivers questions on the demographic data forms and survey questionnaires (stroke caregivers' depression, knowledge, perceived stress, burden, perception of positive aspects of caregiving, self-efficacy, health-related quality of life (HRQOL), and satisfaction with care).

The research staff member will also review the caregivers' Veterans CPRS record to document the Veterans' age, gender, race/ethnicity, category of facility (hospital, community living center, rehabilitation facility) from which the Veteran was discharged to home, length of hospital and/or post-stroke rehabilitation stay, date/location/type of the stroke, number of previous strokes, and healthcare use. The research staff member will document any information in the record related to the Veterans' discharge plans (i.e., treatments, medicines, patient and family education, case management, services).

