The post-test assessments (stroke caregivers' depression, perceived stress, knowledge, burden, perception of positive aspects of caregiving, self-efficacy, health-related quality of life (HRQOL), and satisfaction with care) will be collected at approximately 11 weeks and approximately 19 weeks after the Veterans' discharge. A study team member at the main study site (Gainesville), who will be blinded to the group assignment of the caregivers, will telephone the caregivers to obtain the post-test assessments. The research staff will also review the Veterans' CPRS record and document the Veterans' healthcare utilization since their discharge to home. To minimize loss to follow-up, we will contact participants 24 hours before each post-test assessment to remind them of their scheduled appointment time. We will also mail postcards to enrolled caregivers who we cannot contact after 3 attempts to reduce attrition.

In the event that the RN conducting the intervention or the research personnel conducting the pre-and posttest assessments uncovers that the caregivers are experiencing unmanageable stress, but not severe stress, the research personnel will advise the caregivers to call their assigned VA primary care social workers and primary care clinicians (MD, ARNP, PA) of their Veterans' care team. The research personnel will also give the caregivers the phone number of the VA Caregiver Support Line and other referral sources as needed. If the research personnel assesses that the caregivers are in severe stress or crisis or if the research personnel uncovers that the Veteran has serious changes in his/her health, the research personnel will call the primary care provider/social worker of the Veteran's care team or the local emergency response system (9-1-1). In the event that any abuse or neglect is suspected, study personnel will follow established procedures by oversight agencies, including VHA as directed in the VA Handbook 1050.01, to contact the Office of Inspector General, Office of Investigation, as well as the IRB and the state of Florida Abuse Hotline.

Efforts to improve retention of participants: To improve the chances that participants will complete the project, we will conduct the 11-week and 19-week post-test assessments at times that are convenient to the caregivers.

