| Patient Satisfaction – General Satisfaction Subscale of the Long- Form Patient Satisfaction Question. (PSQ-III) Ware JE, et al., 1976 | The General Satisfaction Subscale consists of 6 items. Responses to items range from 1=strongly agree to 5=strongly disagree. Lower scores indicate greater satisfaction. The subscale has adequate internal consistency and test-retest reliabilities. Validity of the tool has been supported in numerous studies. We selected this tool because it is brief, has good psychometric properties  and is easy-to-read as we found in our previous studies.   | <5
minutes |
| Oberst Caregiving
Burden Scale
Oberst et al, 1991   | This instrument uses a 5-point response scale to measure the perceived amount of time spent and perceived level of difficulty for 15 caregiving tasks. Higher scores indicate more perceived time spent or difficulty with caregiving tasks.   | <8
minutes |
| Problem Checklist   | This instrument was created for the study. The instrument asks caregivers to indicate what problems they or their Veterans are dealing with.   | <5
minutes |
|   | Veteran Measures   |               |
| Demographic and
Health-related variables   | Age, gender, race/ethnicity, facility from which Veteran was discharge to home (i.e., hospital, community living center, rehabilitation), length of post-stroke rehabilitation, location/type of the stroke, and number of previous strokes will be obtained from CPRS review.   | N/A           |
| Functional Abilities – Barthel Index (Caregivers answer this form) Mahoney FI & Barthel D, 1965                                       | The Barthel Index is a frequently used tool to measure functional ability in both clinical and research settings. It has established validity, reliability, and sensitivity. We decided not to use the Functional Independence Measure (FIM), because FIM scores in the Veterans' CPRS records will not coincide when the study assessments will be conducted. Because the FIM items are based on the Barthel Index, we believe this index is a good proxy for the FIM.  | <2
minutes |
| Healthcare Utilization – Unintended hospital bed days of care, number of emergency room visits, number of unscheduled clinic visits   | Data on healthcare utilization will be obtained from the CPRS records.   | N/A           |

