Since the Barthel Index score can be treated as continuous, the analysis plan follows exactly as above in Hypothesis 1. Since the Veteran healthcare utilization measures are count data, the models will be somewhat different. There will be no baseline covariates added to the model, as they are not applicable to the count measures. Analyses will be conducted for the period following baseline data collection to approximately 11 weeks and 19 weeks after baseline data collection. Generalized linear models for count data (such as Poisson or negative binomial regression models, depending on the presence or absence of over-dispersion) will be employed to determine the group effects on healthcare utilization. As before, the site type will be included in the full model and possible site differences will be accounted for. Log link functions will be employed on the count data to create the correct distributional data forms. As before, in order to control for possible sample imbalances resulting from randomization, all models will include covariates for prognostic factors deemed to have significant relationships with response and significant groupwise imbalances. Thus, analyses will be able to compare the groups on the measures of interest while controlling for these factors.

Handling of Missing Data: We should not have a problem with missing data as our data will be collected inperson or over the telephone. Our data collectors will receive extensive training on interviewing and how to politely encourage participants to answer all questions on research instruments. In the event of drop-outs, the missingness mechanism will be explored. If the assumption of Missing Completely at Random (MCAR) or the common assumption of Missing at Random (MAR) are plausible, then little change to the analysis plan is necessary. The mixed models analysis using direct-likelihood approaches will be unbiased and appropriate. Study efficiency (power) will of course be affected by the smaller amount of available information, thus we have inflated the planned recruitment sample size. If the missingness assumptions are not plausible, then Missing Not at Random (MNAR) techniques will be employed and analysis results will be interpreted with caution.

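### The models for emergency and unscheduled clinic visits omit earlier use for a reason that does not hold, at a possible cost in precision

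*Combined protocol and SAP*

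**What the plan says.** Hypotheses #3 in the Data Analysis section covers three utilization outcomes: unintended bed days, emergency room visits and unscheduled clinic visits. They are to be modelled with "Generalized linear models for count data (such as Poisson or negative binomial regression models, depending on the presence or absence of over-dispersion"), using a log link. The analysis window is given as: "Analyses will be conducted for the period following baseline data collection to approximately 11 weeks and 19 weeks after baseline data collection".

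On baseline adjustment the section says: "There will be no baseline covariates added to the model, as they are not applicable to the count measures". It then adds that "all models will include covariates for prognostic factors deemed to have significant relationships with response and significant groupwise imbalances".

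Other parts of the protocol bear on this:

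- The Data Collection section has staff review the Veteran's record at baseline. The list of items ends with "date/location/type of the stroke, number of previous strokes, and healthcare use".
- The Measures table names the same source for the outcome: "Data on healthcare utilization will be obtained from the CPRS records".
- At follow-up, staff are to "document the Veterans' healthcare utilization since their discharge to home".
- The Design paragraph for Aims 1 to 3 says: "In our data analytic plan we will stratify by study sites in addition to controlling for baseline measurements".
- The Hypothesis 1 model defines its baseline term as baseline depression together with time since discharge. The Barthel Index analysis follows that same plan.

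**The concern.** The plan adjusts depression and function for baseline and exempts only utilization, on the ground that a baseline value does not apply to counts. That ground fails if a pre-randomization count exists and the model can take it.

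Veterans differ widely in how much care they use, and earlier use may indicate that tendency. Where it does, leaving it out gives a wider interval for the treatment rate ratio. The sample size was set for caregiver depression only and no power is stated for utilization, so precision there is not known to be ample.

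Read literally, the exclusion also removes time since discharge. Eligibility allows enrolment before discharge or up to 4 months after it, so Veterans can differ materially on that variable.

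**Working it through.** **1. Does a baseline value exist?** The baseline record review lists healthcare use, and the outcome comes from the same record system. The follow-up review also counts from discharge while the analysis starts at baseline. For a Veteran already home at enrolment, some pre-baseline use is therefore on record anyway.

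**2. Can it enter the model?** With a log link, log E(y) = b0 + b1·Group + b2·log(prior count + 0.5) + site terms is an ordinary Poisson or negative binomial regression. Nothing about a count outcome rules it out.

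**3. Does the fallback clause cover it?** The clause needs a significant relation to response and a significant imbalance. Assume imbalance is tested at 5%. Under randomization, prior use would then show a significant imbalance in about 1 trial in 20. In the other 19 (1 − 0.05 = 0.95) it stays out, however strongly it predicts.

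**4. The plan's own figures.** These concern depression (SD 8.2, difference 3.5, 80% power, 5% level, two-sided assumed).

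- n per group = 2 × [8.2 × (1.960 + 0.842)/3.5]² = 86.2, so 87. With 84 per group, power is 79.0%, close to the stated 80%.
- 84/0.70 = 120, which matches the enrolment target.

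No such figure exists for utilization. The 84 completers per arm carry over to the checks below; every other input is an assumption.

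**5. Approximate gain.** One covariate with correlation r to the outcome multiplies the variance by 1 − r², and 84 completers act like 84/(1 − r²).

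| Assumed r | Variance factor | SE factor | 84 per arm acts like |
|---|---|---|---|
| 0.1 | 0.99 | 0.995 | 85 |
| 0.2 | 0.96 | 0.98 | 88 |
| 0.3 | 0.91 | 0.95 | 92 |
| 0.4 | 0.84 | 0.92 | 100 |
| 0.5 | 0.75 | 0.87 | 112 |
| 0.6 | 0.64 | 0.80 | 131 |

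**6. Simulation of visit counts.** Assumptions: 84 per arm, gamma frailty with variance 1 to 2, mean 0.4 to 0.8 events per outcome window, look-back 0.75 to 1.5 times that window, negative binomial fitted by maximum likelihood. The table gives the variance of the log rate ratio, adjusted over unadjusted, with Monte Carlo error of a few percent.

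| Correlation of the Veteran's underlying rate before and after | Variance ratio |
|---|---|
| 1.0 (full persistence) | 0.75 to 0.90 |
| 0.7 | 0.87 to 0.96 |
| 0.5 | 0.93 to 1.01 |
| 0.3 | about 1.0 |

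A second model assumed log-normal rates with log-rate variance 1.0 and a rate ratio of 0.65.

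- Mean count 1.0: the SE moved from 0.245 to 0.244, 0.244 to 0.236 and 0.245 to 0.222 at count correlations of 0.12, 0.28 and 0.48.
- No correlation, mean count 1.0: 0.244 became 0.245, so almost nothing was lost.
- Mean count 2.0, correlation 0.61: 0.206 became 0.171, a variance ratio of (0.171/0.206)² = 0.69. The ceiling therefore rises if events are more frequent than assumed above.

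**7. Simulation of bed days.** With an assumed 0.2 admissions per window and a mean stay of about 6 days, adding log(prior days + 0.5) to the negative binomial model raised the variance by 13% to 35%. Bed days are then mostly zeros with occasional long stays, a different problem from visit counts.

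**The case against.** The strongest objection is that the gain may be nil. For many Veterans the qualifying stroke falls between the look-back and the outcome window, so pre-stroke use may say little about post-stroke use. At a correlation of 0.5 or below in the underlying rates, the simulated gain nearly disappears. This stands, and it is why the range starts at zero. It does not defend the stated reason for exclusion, and adjustment costs almost nothing when the correlation is zero.

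Second, a fixed look-back covers pre-stroke time for a Veteran just discharged and mainly time at home for one discharged 4 months earlier. This also stands. Including time since discharge helps but does not make the two periods the same construct.

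Third, the Design statement on controlling for baseline is general, and the utilization paragraph is a specific exception that announces a different model. That is fair. A reader might infer a contradiction, but the point rests on the mistaken reason, not on a conflict between sections.

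Fourth, the fallback clause could admit prior use if it were significantly imbalanced. It could, although the clause sits awkwardly with the exclusion. What remains is the lost precision when the arms look balanced, and any imbalance short of significance.

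**Conclusion.** The point holds in limited form. The reason given for excluding baseline covariates is wrong, and the fallback is a data-driven rule that does not replace pre-specified adjustment. For visit counts at the assumed 0.4 to 0.8 events per window, the variance reduction forgone is about 0% to 25%. At the upper end, 84 per arm would act like 84/0.75 = 112. Where the trial falls in that range cannot be determined from the documents.

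Four stronger readings are tempting and are not supported:

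- **Bias.** Randomization protects the comparison. The endpoint is secondary and the primary conclusion is untouched.
- **Every utilization comparison loses precision.** For bed days the covariate can make precision worse under plausible assumptions.
- **The Aim 4 budget result is affected.** Aim 4 compares average costs taken directly from the VA cost accounting and Non-VA Medical Care files. It does not use the estimates from these count models.
- **The covariate is ready to use.** The baseline review lists healthcare use without a look-back period or a split by type.

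**What to change.** Delete the sentence saying that baseline covariates do not apply to counts. In its place, pre-specify the following: *The models for emergency room visits and for unscheduled clinic visits will include, whatever the observed balance between arms, log(count + 0.5) of the Veteran's own earlier count of the same type, and time since discharge. The earlier count will be taken from CPRS over one fixed look-back before baseline, the same length for every Veteran, excluding the index stroke stay.*

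Do not require the earlier count in the negative binomial model for bed days. Time since discharge is already part of the baseline term in the Hypothesis 1 model, so it needs no new data.

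The cost is a short change to the analysis text and a revised baseline record form that fixes the look-back and separates use by type. This means slightly more abstraction. The sponsor must choose the look-back length, since the documents give none.

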#### Research Design and Methods (Aim #4)

Research Question: What are the budgetary impacts associated with the intervention and how do these costs compare to usual care?

Data collection & measures: We will obtain cost data in the VA Managerial Cost Accounting System (MCAS) (formerly DSS) National Data Extracts (NDE) (total, nursing, pharmacy, laboratory, etc.) by fixed and variable categories and the Non-VA Medical Care files, supplemented by the direct measures (i.e., microcosting) of the intervention as necessary.

Research Question: What are the budgetary impacts associated with the intervention and how do these costs compare to the costs of usual care?

The budgetary impact of this intervention will consist of two parts: (1) the incremental cost of the intervention itself over and above usual care, and (2) the impact of the intervention on healthcare utilization. To determine the incremental costs of the intervention, we will use micro-costing techniques (viz., direct measurement and pseudo-billing) combined with average costing to determine the average staff time, wage, space, and equipment costs associated with the intervention. The micro-cost estimate for the transition-to-home and inhome sessions will use the average elapsed time of such sessions along with an estimate of the average national wage of the type of nurse most likely to deliver the intervention in the field.

To determine the intervention's impact on the costs of healthcare utilization, we will rely on ISPOR's 2014 budgetary impact analysis guidelines. Data on VA-funded utilization costs will be obtained from MCAS)  and the Non-VA Medical Care files. We will tabulate all costs from these sources for study enrollees over the period of the study, calculate the difference between intervention and usual care average costs and test for the statistical significance of this difference using the Z-score method proposed by Zhou.

The final step in determining the budgetary impact of the intervention will combine parts 1 and 2 to determine the complete impact of the intervention on the VA budget. While the incremental cost of the

intervention (part 1) will be positive, the impact of the intervention on the costs of VA utilization will likely vary directly with the impact of the intervention on VA utilization.

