## **Randomization:**

The proposed study will use a two-group randomized design with 3 assessment points (baseline, approximately 11 weeks, and approximately 19 weeks). Following baseline assessments, the participant will be randomly assigned to one of the two study groups (Intervention or Usual Care). The Pocock-Simon covariate adaptive randomization procedure will be used so that there will be approximately equal number of subjects assigned to the two groups within each covariate level (depressed or not and high or low ADL) and within each study site. The statistician will develop the randomization scheme and share it with the project coordinator and a research staff member at each site. When a caregiver is enrolled in the study, this staff member at site will obtain the group assignment for that caregiver from the randomization system.

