implementing the intervention and discuss protocol issues. To monitor the delivery of the intervention, we will listen to each research nurse's first one or two transition-to-home sessions to identify any fidelity issues at the beginning of the project. Following this initial monitoring, we will periodically listen to the remaining sessions, making sure that we have fidelity checks during the beginning, middle, and end of the first component of the intervention. We will also ask the research nurses to track the number of minutes they spend with each participant and to keep detailed notes of any deviations from our study protocol that occur during the transition-to-home sessions. The PI and project coordinator will discuss the deliveries of the intervention and evaluate adherence to study protocols, noting all deviations on a form. Feedback will be provided to the research nurses.

In a similar fashion, we will monitor the in-home sessions (in the intervention) that are conducted via the RESCUE messaging center. We will review the first two "exact correspondences" of the caregiver and nurse to identify initial, fidelity issues. After this assessment, we will periodically review the exact correspondences between the caregiver and nursing on the messaging center to ensure that we have fidelity checks throughout the project. The research nurses conducting the in-home sessions will also keep detailed notes of any deviations in protocol that occur during the in-home sessions. The PI and project coordinator will review the fidelity check data and provide feedback, as needed, to the main study, research nurse.

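### Aim 4's only specified test covers utilization cost, with no covariates; the combined budget impact that answers its question has no stated test or interval

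*Combined protocol and SAP*

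**What the plan says.** The Aim 4 question, under Specific Aims and again under Research Design and Methods (Aim #4), is what the intervention costs and how that compares with usual care. The Aim 4 section defines budget impact in two parts: "1) the incremental cost of the intervention itself over and above usual care, and (2) the impact of the intervention on healthcare utilization".

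- **Part 1** comes from micro-costing "combined with average costing to determine the average staff time, wage, space, and equipment costs associated with the intervention". The session estimate "will use the average elapsed time of such sessions along with an estimate of the average national wage" for the kind of nurse expected to deliver the programme in practice.
- **Part 2** uses recorded costs: "Data on VA-funded utilization costs will be obtained from MCAS" and from the Non-VA Medical Care files. On these the plan will "calculate the difference between intervention and usual care average costs and test for the statistical significance of this difference using the Z-score method".
- **The sum:** "The final step in determining the budgetary impact of the intervention will combine parts 1 and 2 to determine the complete impact". The section then says that part 1 will be positive and that utilization costs will probably follow utilization, and it ends. It states no test, interval or sensitivity analysis for the sum.

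The Aim 4 section names no covariate or site term. Elsewhere the plan does. Allocation is balanced "within each covariate level (depressed or not and high or low ADL) and within each study site" (Randomization). The design section for Aims 1 to 3 commits to stratifying by site and controlling for baseline. The count models for utilization under Data Analysis include site and any imbalanced prognostic factors.

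**The concern.** The quantity that answers the Aim 4 question is the sum of the two parts, but the only planned p-value belongs to one of them. The omitted part has a known sign: it always reduces a saving. A reader of the results would therefore see a significance statement for utilization cost beside a combined figure with no stated uncertainty, and could carry the first over to the second. The plan says its primary and secondary findings will inform translation into VA practice, and a budget decision of that kind needs the net figure with its uncertainty.

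The lack of specified covariates is a separate and smaller matter. The plan says usual care may differ at Tampa and handles site in the other quantitative aims, yet specifies nothing for the costs of the same utilization that it models with site under Aim 3.

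**Working it through.** **Inputs.** Aim 4 states no sample size, power, cost SD, intervention cost or expected saving, so there is no plan figure to reproduce. From Rationale for Study Sample Size, 120 are enrolled per group with 30% dropout, and 120 × 0.7 = 84 complete. Those numbers were set for depression; 84 is used below only for scale. The Aim 4 section gives neither a significance level nor sidedness, so two-sided 5% is assumed. Every cost value below is an assumption.

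**Formula.** Let D be the utilization saving, SE its standard error, and c the intervention cost per caregiver, treated as a fixed average as in the plan. Then

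- utilization z = D/SE
- net z = (D − c)/SE = utilization z − c/SE

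So the utilization saving is significant, and a net saving is not shown, whenever 1.96 < utilization z < 1.96 + c/SE. That band exists for any positive c.

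**Example.** Take utilization z = 2.0 (p = 0.046) and c equal to a quarter of the saving. Then c/SE = 0.25 × 2.0 = 0.5, and net z = 1.5 (p = 0.134).

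**Range over c/SE.** The last two columns suppose that the true utilization saving only equals c, so the true net impact is zero. The chance of a significant net saving is then 2.5%, and the last column is 1 − 0.025/(chance of a significant utilization saving).

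| c/SE | Net p if utilization p = 0.05 | Net p if utilization p = 0.01 | Chance of a significant utilization saving | Share of those with no significant net saving |
|---|---|---|---|---|
| 0.1 | 0.063 | 0.013 | 3.1% | 20% |
| 0.25 | 0.087 | 0.020 | 4.4% | 43% |
| 0.5 | 0.144 | 0.038 | 7.2% | 65% |
| 1.0 | 0.337 | 0.115 | 16.9% | 85% |

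**In money terms.** SE = SD × √(2/n), with n = 84 per arm and a utilization saving exactly at the 5% threshold.

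- SD 10,000: SE = 1,543 and the threshold saving is 1.96 × 1,543 = 3,024. With c = 500, net z = 1.96 − 0.324 = 1.64 (p = 0.10). With c = 1,000, net z = 1.96 − 0.648 = 1.31 (p = 0.19).
- SD 40,000, c = 250: SE = 6,172, c/SE = 0.041, net p = 0.055. The difference is negligible.
- SD 5,000, c = 1,000: SE = 772, c/SE = 1.296, net z = 0.66 (p = 0.51). The difference is large.

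**Adjustment.** If covariates explain a share R² of the cost variance, the SE shrinks by the factor √(1 − R²): 0.894 at R² = 0.2 and 0.837 at R² = 0.3, or about 11% to 16% smaller. These R² values are assumed.

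**The case against.** The plan does not leave the saving to stand alone. It commits to reporting the combined impact and says openly that part 1 will be positive, and Aim 4 has a research question, not a hypothesis. It also relies on published budget impact guidelines for the utilization part. Those may call for uncertainty analysis, but their content is not in the documents. This stands, and it is why the point says that no interval is specified, not that none will be given.

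A reader might infer that Aim 4 cannot tell whether net cost differs from zero. The documents do not support that: if part 1 is a fixed average, the net interval is the utilization interval shifted by c, and can be had from planned outputs. The gap is that the plan does not say this will be done. Nor does it allow for sampling error in part 1, which would come from averaging session times observed in the trial.

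A reader might also infer that the Z-score method has the wrong error rate for skewed costs or costs with zeros. The plan names the method without describing it, so nothing can be concluded about its validity. Read literally, it compares average costs.

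Nor does the missing adjustment cause the missing interval or bias the comparison. Under randomization it costs precision.

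Finally, the plan prices average session time at a national wage because it wants the cost of delivery in routine practice, and using each caregiver's own trial cost might seem to change that quantity. Pricing recorded minutes at the same national wage keeps it: average minutes times a constant wage equals the average of minutes times wage, provided the plan means sessions actually delivered, which it does not state. Space and equipment are planned only as averages and can stay so.

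**Conclusion.** The point holds as a mismatch between test and question. The one specified test concerns utilization cost. The net figure, which answers Aim 4, has no specified test or interval, and no covariates are specified for the test there is. Because part 1 is positive, the two conclusions can differ in one predictable direction. How often they would differ depends on c/SE, which the documents do not allow anyone to compute: in the examples above, a utilization saving just at the threshold has a net p anywhere from 0.055 to 0.51. The missing adjustment is a matter of precision, worth an SE about 11% to 16% smaller under an assumed R² of 20% to 30%. Aim 4 is secondary, so this should be changed but does not threaten the primary result.

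**What to change.** In Research Design and Methods (Aim #4):

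1. Make the between-arm difference in arithmetic mean net VA cost the Aim 4 estimate. For each dyad in the intervention arm, net cost is utilization cost plus micro-costed intervention cost: recorded nurse and messaging minutes at the plan's national wage, plus average space and equipment cost. In usual care nothing is added.
2. Adjust for site, ADL level, baseline depression and baseline healthcare use, and state the look-back period for that last covariate.
3. Report a bootstrap 95% confidence interval for the net difference, show utilization cost as a component, and give sensitivity to wage and session time.

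The inputs are already planned. Under Fidelity Considerations the nurses are to "track the number of minutes they spend with each participant", and messaging minutes are logged in the in-home component. The stratification factors are in the randomization, and Data Collection lists healthcare use among the items taken from the record at baseline. Data Analysis calls baseline covariates inapplicable to the utilization counts, so the text should say that prior healthcare use enters the cost model as a covariate.

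The price is a change of wording, a little more analysis, and possibly a less favourable net result than the utilization comparison alone would show.
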